12.0 Statistical Considerations

[name] of the College of Nursing statistician will conduct all analyses. The apriori stated analysis is listed below.

This is a pilot study for feasibility. For these pilot data we will emphasize descriptive statistics such as means, standard deviations, effect sizes, medians, interquartile ranges, frequencies, and percentages to demonstrate the feasibility of recruitment, adherence, and retention, treatment effects over time, and proof

of concept. Our statistical approach for a full trial of these hypotheses will be Generalized Linear Mixed Models (GLMM) with an identity link function for a continuous outcome or a logit link function for a binary outcome. Conceptually, GLMM is a more advanced version of repeated measures ANOVA that can account for potential correlation among multiple measurements over time while having flexibility in fitting outcomes with different distributions (such as normal, binomial or Poisson, etc.). One advantage of this approach over repeated measures ANOVA is that there is no assumption that participants are measured at every, or even the same, time points. Therefore, these models are very flexible at handling missing data. Participants who have a missing observation are not excluded, thus, this produces the intention to treat (ITT) full information maximum likelihood (FIML) model. Conducting these models on pilot data help with sample size calculations for a future R01 submission.

This is a pilot study investigating the feasibility and proof-of-concept. There is no power-calculation for this study: This study may not be powered to find statistically significant differences between groups due to the smaller sample size. Based on previous studies, we do expect to find at a minimum a trend for improvement cognitive function and brain structure. We expect to be able to use these data for determination of the necessary sample size for detection of significant differences between groups

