Anticipated Benefits: **This is a pilot study for feasibility** and no benefits should be expected. Walking exercise training has been associated with significant improvement in fitness (aerobic capacity), blood pressure, and ability to perform activities (physical function). The effect of exercise training on cognition is promising, but currently unknown.

Subject population: We anticipate randomizing 72 men and women with and without CKD between 60 and 80 years of age with no contraindications to moderate-intensity exercise that answered “yes” to the question “Do you feel like your memory or thinking skills have gotten worse recently?”. (please see detailed inclusion/exclusion criteria, section 4), In order to achieve this we anticipate sending 2000 letters to potential participants at UIC.

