3.0 Objectives/Aims

This is a pilot study for feasibility. The objective of this study is to test the hypothesis that older participants with moderate/severe chronic kidney disease (CKD) and preclinical cognitive impairment randomized to a 6-month home-based exercise program (n=12), will improve cognitive functioning and white matter integrity (WMI), compared to participants in a usual care control group (n=12). Our central working hypothesis is that the accelerated cognitive decline that occurs in CKD results, in part, from a vascular-dysfunction induced impairment of white matter integrity that is superimposed on a neurodegenerative process, and that exercise training may provide a cerebro-protective effect by improving systemic and cerebral vascular health.

Aim 1: Determine the feasibility and preliminary efficacy of a 6-month home-based exercise program to improve or maintain cognitive function in older participants with moderate/severe CKD and preclinical cognitive impairment, compared to usual care control group.

Hypotheses: Participants in the exercise group compared to the usual care control group at 6-months will:

- H1a. Demonstrate a higher score on composite global cognitive functioning.
- H1b. Demonstrate higher scores on executive functioning, learning/memory, and attention/information processing.

Aim 2. Determine the cerebro-protective effect of a 6-month exercise program compared to usual care on white matter integrity as quantified by Diffusion Tensor Imaging (DTI)-derived MRI measures of mean diffusivity (MD) and fractional anisotropy (FA). Intact white matter is important because it allows the brain to function properly and these are indices of white matter integrity.

- H2a. Participants in the exercise group will demonstrate an improvement in overall white matter integrity as measured by DTI, i.e., lower MD and higher FA, compared to control.

- H2b. Change in cognitive function will be positively correlated with change in WMI.

Aim 3 (secondary MRI outcomes): Determine the cerebro-protective effect of a 6-month exercise program compared to control on hippocampal volume and cerebral blood flow.

Hypothesis: Participants in the exercise group will have a larger hippocampal volume and improved cerebral blood flow post 6-month intervention, compared to the control group.

Study Duration: 12 months. Study duration for enrolled participants is anticipated to be 27 weeks.

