The monthly meetings (once per month) will occur at months, 1, 2, 3, 4, and 5 following randomization. The PI and study staff will continue to work with the participants to assess their readiness to do exercise; 2) address perceived barriers to exercise, and 3) provide support and address concerns related to the exercise program. The meetings will last 30 minutes. We will assess for any adverse events during the bi-weekly phone calls using the document title "Adverse Event Monitoring". The total number of visits in the exercise group is 11.

Usual medical care control group

The usual care group will receive standard instructions on exercise for patients with kidney disease. These documents are titled "Exercise Recommendations" and "work effort scale". This is similar to what is commonly done in clinical practice. The control group will not receive an exercise prescription or heart rate monitor. Participants will be contacted via phone biweekly to answer any questions and ensure continued study participation. In order to minimize any feeling of disenfranchisement in the control group we will offer them the exercise training prescription following all post-test data collection procedures. The usual care group will NOT meet monthly. We will assess for any adverse events during the bi-weekly phone calls using the document title "Adverse Event Monitoring". The total number of visits for the usual care group is 5.

Ten participants with an eGFR of >60 ml/min will only undergo baseline testing and not partake in the intervention or follow up. We will ask if the participants with an eGFR >60 ml/min prefer to only to the baseline versus intervention.

Follow-up testing will occur at 24 weeks over 2 visits about 1 week apart. During the follow up testing we will ask participants to perform one 6-minute walk test and the short physical performance battery, and the NIH toolbox measures as described above, as well as completing the questionnaires and imaging procedures described above.

During the 24-week visit we will query patients using structured interviews and open-ended questions as to whether participants liked the independent home-based walking program. Study satisfaction will be assessed using a likert scale and open-ended question at the end of the 24 week follow up test..

Physical activity and exercise monitoring and Assessment of Adherence to Exercise Rehabilitation Program (fidelity of treatment):

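### The mixed model to be run on the pilot data does not say how baseline enters, and the planned sample size and randomised population contradict each other

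*Combined protocol and SAP*

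**What the plan says.** Sections 9.0 and 12.0 carry the same analysis text. For the pilot they stress descriptive summaries, including standard deviations and effect sizes. The mixed model is introduced for a later study: "Our statistical approach for a full trial of these hypotheses will be Generalized Linear Mixed Models (GLMM". It is characterised as follows: "Conceptually, GLMM is a more advanced version of repeated measures ANOVA that can account for potential correlation among multiple measurements over time". On missing data the text says: "Participants who have a missing observation are not excluded, thus, this produces the intention to treat (ITT) full information maximum likelihood (FIML) model". The model is then brought back to the pilot: "Conducting these models on pilot data help with sample size calculations for a future R01 submission".

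Neither section gives the fixed effects, the treatment contrast, the role of baseline, the covariance structure or a degrees-of-freedom method. Section 6.0 measures the cognitive and imaging outcomes before the intervention and at 24 weeks. Section 3.0 introduces the Aim 1 hypotheses with "Participants in the exercise group compared to the usual care control group at 6-months will", followed by higher scores.

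On size, Section 1.0 says: "We anticipate randomizing 72 men and women with and without CKD between 60 and 80 years of age". Section 3.0 describes an exercise arm of 12 people with moderate/severe CKD, "compared to participants in a usual care control group (n=12". Section 6.0 adds: "Ten participants with an eGFR of >60 ml/min will only undergo baseline testing and not partake in the intervention or follow up". Section 12.0 states that there is no power calculation, so no derivation shows which number is meant.

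**The concern.** With one baseline and one follow-up measurement, the handling of baseline defines the treatment effect. The repeated-measures ANOVA description suggests a group-by-time interaction. With complete data and unconstrained means, that interaction is the between-arm difference in mean change. Adjusting the 24-week value for baseline uses the same data and is usually more precise. The text leaves the choice open, so it could be made after results are seen.

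At stake are the precision of the pilot effect estimate, the variance and correlation passed to the next sample size, and the method carried into the full trial, for which the same model is named. Separately, recruitment, retention and precision cannot be judged when the plan gives two sizes and two populations.

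**Working it through.** **Inputs.** 12 per arm (Section 3.0), or 36 per arm (72 from Section 1.0, halved under the 1:1 allocation in Section 6.0). Two time points (Section 6.0). The documents give no baseline/24-week correlation r, so 0.6 to 0.8 is assumed and 0.9 is shown as a check. Equal SDs at both visits are assumed at first.

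**1. Change score against baseline adjustment, complete data.** With n per arm, in units of 2 × SD² / n:
- change score: 2(1 − r)
- baseline-adjusted: (1 − r²) × (1 + 1/(2n − 4)), where the factor is 1.05 at n = 12 and 1.0147 at n = 36

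| r | change | adjusted, n=12 | ratio | adjusted, n=36 | ratio |
|---|---|---|---|---|---|
| 0.6 | 0.80 | 0.672 | 1.190 | 0.649 | 1.232 |
| 0.8 | 0.40 | 0.378 | 1.058 | 0.365 | 1.095 |
| 0.9 | 0.20 | 0.1995 | 1.003 | 0.193 | 1.037 |

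The two are equal when 1 + r = 2/1.05, that is r = 0.905 at n = 12. Above that, the change score is slightly better.

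Simulation at n = 12 (3,000 draws each) agrees. The common-baseline-mean model has the same variance as ANCOVA, and the interaction has 1.205 (r = 0.6) and 1.065 (r = 0.8) times that variance.

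**2. Missing data.** With an assumed 2 of 12 per arm missing 24 weeks, simulation of the same size gave ratios of 1.12 and 1.02. Approximate arithmetic gives a similar answer:
- adjusted: (1 − r²)(2/10)(1 + 1/16) = 0.136 and 0.0765
- interaction: 2[(1 − r²)/10 + (1 − r)²/12] = 0.155 and 0.0787
- ratios: about 1.14 and 1.03

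Either way the advantage is smaller than with complete data.

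**3. Unequal SDs.** If the 24-week SD is k times the baseline SD, the change-score variance becomes 1 + k² − 2rk and the adjusted variance k²(1 − r²) × 1.05 at n = 12. At r = 0.8:
- k = 1.2: 0.52/0.544 = 0.96
- k = 0.8: 0.36/0.242 = 1.49

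So 6-19% is not a bound in either direction.

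**4. ML against REML.** If the likelihood wording means literal maximum likelihood, the residual variance is multiplied by (2n − 2)/2n. That is 22/24 = 0.917 (8.3% low) at 12 per arm and 70/72 = 0.972 (2.8% low) at 36. For comparison, the 95% limits for the adjusted SD are 0.77 to 1.43 times the estimate at 12 per arm (21 df) and 0.86 to 1.20 at 36 (69 df). For an assumed 0.5 SD target needing 64 per arm, the ML shift at 12 per arm is to 64 × 0.917 = 59. The SD limits span 64 × 0.77² = 38 to 64 × 1.43² = 131.

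**5. Sample size.** Section 3.0 gives 12 + 12 = 24; Section 1.0 gives 72. Adding the ten baseline-only participants to 24 gives 34, and removing them from 72 gives 62, so neither step reconciles the two. The 95% half-width for an unadjusted comparison is 2.074 × √(2/12) = 0.85 SD at 12 per arm and 1.994 × √(2/36) = 0.47 SD at 36. The populations differ too: with and without CKD in Section 1.0, moderate/severe CKD in Section 3.0.

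**6. Timing of baseline.** Section 6.0 randomises on completion of visit 3 but places the exercise group's education session during visit 2. A common baseline mean needs baseline to precede allocation. The Table 1 cognitive tests are done at visit 1 and are unaffected. The visit 2 imaging and visit 3 measures are affected until the text is reconciled.

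**The case against.** The strongest reply is that this is a feasibility pilot. It emphasises description, disclaims power and promises no test, interval or primary contrast, so missing model detail is a gap rather than an error. That is fair and sets the weight of the point. It does not remove it, because the plan says the models will be run on the pilot data for a stated purpose. If the intended model already constrains the baseline mean, the baseline gain is nil, and one sentence saying so would settle the matter. The precision gain also rests on an assumed correlation and equal SDs, as shown above.

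Three stronger readings are tempting, and the documents support none of them:
- A reader might infer from the Aim 1 wording that raw 24-week means will be compared. That wording is a directional hypothesis, which an adjusted difference also addresses. Section 3.0 speaks elsewhere of improvement and change, and Section 12.0 of effects over time.
- A reader might infer that intervals will be too narrow because of maximum likelihood with normal limits. The likelihood phrase occurs in a sentence about keeping participants with missing data and may mean only that. No section mentions normal limits.
- A reader might subtract the ten baseline-only participants from the 72. Section 1.0 speaks of 72 randomised, and the ten take no part in the intervention, so read plainly they lie outside it.

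**Conclusion.** The point holds as a low-priority improvement on the model and as a firm inconsistency on size.

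**Model.** The role of baseline is unspecified. If the contrast is group-by-time, its variance exceeds the baseline-adjusted variance by about 6-19% at 12 per arm and 10-23% at 36. This assumes r of 0.8 to 0.6, equal SDs and complete data. With 2 of 12 per arm missing the excess is about 2-12% in simulation. At 12 per arm there is no gain near r = 0.9 and a slight loss above about 0.905, and unequal SDs can move the figure either way. REML is a minor safeguard: the ML shortfall arises only on a literal reading and is small beside the sampling error of the pilot SD.

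**Size.** The conflict between 72 and 12 per arm, and between the two populations, rests on no assumption. Both statements cannot be right.

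**What to change.** In Sections 9.0 and 12.0, for the continuous Aim 1-3 outcomes, name the treatment effect as the 24-week between-arm difference adjusted for baseline. Estimate it from a mixed model with a common baseline mean, fitted by REML with Kenward-Roger degrees of freedom. This keeps participants with a missing observation in the analysis, as the plan intends, although someone with no 24-week value adds little to the estimated effect. Kenward-Roger is meant here for the identity-link outcomes and does not carry over directly to the logit-link ones. For the later sample size, report the adjusted SD with its confidence interval and the baseline/24-week correlation.

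State one sample size and one randomised population in Sections 1.0, 3.0 and 6.0, and say whether the ten baseline-only participants count within it. Reconcile the Section 6.0 statements on the timing of randomisation and of the education session.

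The cost is wording only, with the same data and visits. If intervals are reported, they will be slightly wider than maximum-likelihood intervals with normal limits for the same contrast: (2.074/1.960) × √(24/22) = 1.105, about 10% at 12 per arm, and (1.994/1.960) × √(72/70) = 1.032, about 3% at 36. Where baseline adjustment improves precision, it offsets part or all of this.

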13.0 Regulatory Requirements

13.1 Informed Consent

Each interested subject will be mailed a copy of the consent form 1 week prior to scheduling the initial consent visit. This will be done to allow potential subjects sufficient time to consider participation. Informed consent will be obtain in the CON Health Research Laboratory 229 at the baseline visit. Informed consent will be obtained using procedures and documents understandable to the subject. Individuals who are unable to give informed consent will be excluded from participation in this research. All study personnel will have received the required UIC CITI and HIPAA training prior to initiation of the study. The PI ([name]), and the study manager will obtain consent. Subjects that contact the study team will be given as much time as they feel necessary to decide if they would like to participate. Subjects will be encouraged to ask any questions at any time throughout the course of the study. Research personnel will be available to answer these questions. Subjects will be informed that participating in this research is voluntary. Subjects will be informed that they may withdraw from the research at any time without penalty. Patient providers are not part of the study team. Informed consent documents will be kept in a locked file cabinet in a locked office separate from other study documents. Only the PI ([name]) will have access to these files.

We have requested approval for a waiver of consent for recruitment purposes only to identify potential subjects from the medical records. We will only obtain patients name, address, medical record number, and whether they have the ICD code for diagnosis of CKD. This is minimal risk. We are requesting an alteration of consent to conduct the telephone screening for all potential subjects that have expressed an interest in the study and would like to be contacted by the study team. The telephone screen will be used to determine initial eligibility and to schedule the consent visit. The telephone screen is minimal risk. The only potential risk to participating in the telephone screen is loss of confidentiality. The initial telephone screening and interview is a component of the study and involves an assessment to determine if individuals potentially interested in participating meet the preliminary qualification criteria and attests to their interest in participating in the entire study. Candidates who meet the screening criteria and agree to participate will be invited to schedule an initial visit during which formal written consent processes will be executed. The telephone screening obviates the need for unnecessary visits to UIC. This represents an alteration in the consent process

13.2 Subject Confidentiality

Precautions to protect subject privacy will be taken throughout the course of the study. All telephone conversations with potential subjects will be conducted in a private setting. Face to face conversations will be conducted within a private setting within the College of Nursing clinical health laboratory with private rooms. Strict procedures will be put in place to minimize the risk of breach of confidentiality. All subjects will be assigned a study code. The master list of the subject's name and the linked code will be kept by the study manager in a locked file cabinet in a locked office. All information provided by subjects will be kept strictly confidential and will not be reported on an individual basis. None of the information provided by subjects will become part of the medical record. Hard copy data will be stored in a locked office, and electronic data will be stored on a password-protected computer. Hard copy and electronic data will be coded, with the master list kept separately in a secure file in the principal investigator's office. A HIPAA authorization form will be developed for this study to use/disclose protected health information. Subjects will be asked to sign the HIPAA consent form. Subjects who refuse to agree to the HIPAA authorization will not be able to participate in this study. Study data will be coded in numerical order (e.g. CKD001, CKD002 etc.). The link to the code will be maintained by the project manager and will be kept in a locked file cabinet in a locked office separate from study data. An electronic copy of the masterfile will be kept in a folder, separate from the data and study forms, on a UIC secured drive. The project manager and PIs will have access to the code. The link to identifiers will be destroyed after 6

years. The study statistician will have access to the de-identified database for analysis purposes.

13.3 Unanticipated Problems

- All study-related, serious, unanticipated adverse events will be reported to the IRB within 48 hours of discovery. Other unanticipated events will be reported to the IRB at the time of continuing review. We will comply with university policies and procedures regarding any unforeseen identifiable data loss.

